**Sample and Setting.** The proposed study will follow a prospective cohort ( $N = 120$ ) of racially and economically diverse VLBW infants for 6 weeks following birth. The infants will be born to mothers who are English or Spanish speaking and who are 18 years of age or older. VLBW infants will be sampled by convenience from the neonatal intensive care unit (NICU) at Shands Children's Hospital, a Level III tertiary care center. The hospital is part of the University of Florida and includes a 52 bed NICU. The hospital catchment area encompasses north central Florida and southern Georgia, a predominantly rural and semi-rural population. Approximately 100-110 VLBW infants are delivered there per year. In the preliminary study, 70% of mothers consented for the study. Inclusion criteria for the infants are as follows: (1) born at 32 weeks or less of gestational age, (2) birth weight equal to or less than 1,250 grams, and (3) infant receiving some enteral feedings by 72 hours of age and parenteral feedings by 24 hours of age. Exclusion criteria for the infants are as follows: (1) congenital or chromosomal abnormalities, (2) complex congenital heart diseases and congenital anatomic gastrointestinal abnormalities, (3) Infants will be withdrawn from the study if any of the following occur: grossly bloody stools, radiologic evidence of NEC, or other intestinal complications such as perforation.

**Sample Size Determination / Power Analysis.** In the preliminary study, 40 premature, VLBW infants had a mean enteral intake at 14 days of 72 mL/kg/d ( $SD=65$ ). To detect a 50% improvement to 108, we would require 104 evaluable subjects in a non-sequential design for Primary 1.1 to achieve 80% power at  $P=0.05$  (two-sided). To accommodate one interim analysis, we employed the minimax method of Shuster et al (2002), with first look after 66 evaluable subjects have been accrued. If  $|Z|>2.28$  we shall stop for significance. If  $|Z|<1.12$ , the study will be reviewed for possible futility. There will be no stopping for futility. Otherwise, the study will accrue 120 evaluable subjects (54 more). No competing two stage design can achieve a lower worst case scenario average sample size than this one's 89 evaluable. Intent-to-treat will be followed as closely as possible. However, to accommodate dropouts including deaths (15%) and infants who develop NEC (7%) we expect to accrue 160 subjects.

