**Research Procedure.** The procedures used in this study will be the same as those successfully used in the preliminary study. Following consent by the mothers, infants will be randomized, and baseline demographic data will be collected from their medical charts. Over the first 6 weeks of life the following additional information will be collected at specified time periods from their medical charts: weekly enteral intake, days to full enteral feedings (120 mL/kg/d), hours of PN, evidence of PNALD (level of direct bilirubin, alkaline phosphatase, aspartate aminotransferase (AST) and alanine aminotransferase (ALT)), growth indices (weekly weight, head circumference and length), medications, hours with a CVL, episodes of presumed or culture proven LOS (occurring > 7 days of life), days to discharge, evidence of stage 2 or greater NEC, evidence of aspiration pneumonia on chest radiograph, episodes of ventilator associated pneumonia and guaic status of stools. Additionally, one stool sample will be collected at 3 and 6 weeks to test for fecal calprotectin levels. 1mL of blood will be collected during a routine blood draw between 7 and 14 days of life to test for serum gastrin and motilin levels. If ventilated, tracheal aspirate samples will be collected on days 1, 3, 5, 7, 14, 21, 28 and 35 from routine tracheal aspirate suctioning. As kangaroo care is a potentially confounding factor, episodes and duration of kangaroo care between mother and infant will be recorded on the Kangaroo Care log sheet located at the infant's bedside by either the mother or the nurse. See Table 1.

**Aim 1.** The primary aim of this study is to determine the risks and benefits of aspirating RGC and the clinical benefits of omitting aspiration of RGC prior to enteral feedings on the nutritional outcomes of premature VLBW infants. Both groups will have a sign placed on their isolettes stating which group they are assigned to and whether the nurse should or should not aspirate RGC. Although already documented on the infant's flow sheet, the sign will also include an area for the nurse to document the OG/NG insertion depth. Those personnel who are not involved with the study infants will be unable to be blinded since information regarding gastric residual volume and color is placed in the chart by the nursing staff and monitored by clinicians making decisions regarding enteral feeding plans. The PI is a neonatal nurse practitioner in the NICU

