**Aim 3.** Aim 3 will determine the effect of routine RGC aspiration on gastrointestinal function as evidenced by gastrointestinal peptide activity. Serum levels of gastrin and motilin will be measured on all infants between 14 and 21 days depending upon the timing of a routine blood draw. Since all GRCs are not discarded, waiting until between 14-21 days will allow adequate time for potentially one or more GRC to be discarded. 1 mL of blood will be taken during a routine blood test. All samples will be sent to the laboratory at Shands Children's Hospital at the University of Florida for testing, and lab values will be extracted and recorded by the project coordinator.

**Statistical Analysis.** Data will be entered into the RedCap system by the research assistant. For the primary hypothesis (P1.1), the total weekly enteral intake will be compared between the two randomized treatment groups via a two-sided Welch-corrected T-test. For sample sizes of this magnitude, the central limit theorem assures us that this is an assumption-free analysis, even if the underlying population variances differ. An interim analysis of P1.1 will also be done as described in the Power Analysis section below. Secondary hypotheses S1.1-S1.7 will be tested in the same manner as the primary hypothesis P1.1. For secondary Hypothesis S2.1 (S3.1), [S3.2], we shall compare the personal fractions of positive stools (gastrin levels) [motilin levels] respectively via two-sided Welch-corrected T-tests. For secondary hypothesis S2.2, we shall use a repeated measures analysis of variance to compare the groups with respect to week 3 and week 6 calprotectin levels. . Actual P-values will be reported, and each hypothesis will be accompanied by a point estimate and 95% confidence interval estimate for effect size. For descriptive purposes, a P-value of under 5% will be declared significant. The study is powered strictly around the primary hypothesis P1.1. Withdrawal rates will be compared between the treatments in a tertiary manner using survival analysis (time to withdrawal), via a logrank test.

**Expected outcomes.** Based on the preliminary study, it is reasonable to expect that infants who do not receive routine aspiration of RGC will have better nutritional outcomes, evidence of less gastrointestinal bleeding and inflammation, and improved gastrointestinal function.

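### The calprotectin analysis (S2.2) has no rule for a missing stool sample; a classical repeated measures ANOVA would discard valid week-3 values and can bias the group comparison

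*Combined protocol and SAP*

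**What the plan says.** Under Statistical Analysis, the method for secondary hypothesis S2.2 is a single sentence: "we shall use a repeated measures analysis of variance to compare the groups with respect to week 3 and week 6 calprotectin levels". Under Research Procedure, "one stool sample will be collected at 3 and 6 weeks to test for fecal calprotectin levels", so each infant contributes at most two values.

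Under Sample and Setting, "Infants will be withdrawn from the study if any of the following occur: grossly bloody stools, radiologic evidence of NEC"; other intestinal complications, such as perforation, are a further trigger. Under Sample Size Determination / Power Analysis, the sponsor writes that "to accommodate dropouts including deaths (15%) and infants who develop NEC (7%) we expect to accrue 160 subjects", and also that "Intent-to-treat will be followed as closely as possible".

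The document gives no rule for an infant with one stool sample, no imputation and no sensitivity analysis. The only analysis of withdrawal is a tertiary logrank test of time to withdrawal. Statistical Analysis promises a point estimate and 95% confidence interval for each hypothesis, and says that the study is powered only for P1.1.

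**The concern.** A classical repeated measures ANOVA needs a complete pair. An infant with a week-3 stool who dies or is withdrawn before week 6 then leaves the analysis altogether, although a valid outcome value was measured.

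The withdrawal triggers are bleeding and gut injury, and Aim 2 is about gastrointestinal bleeding and inflammation. It is therefore plausible that infants lost after week 3 have higher calprotectin than those who stay. If so, the complete pairs are a selected sample. The stakes are lost precision in every case where loss falls after week 3, and a distorted group difference in some of them.

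**Working it through.** **The plan's own figures.** None concerns calprotectin. The stated 104 evaluable infants is for enteral intake and does reproduce: 2 × (1.960 + 0.842)² × 65² / 36² = 51.2, so 52 per arm and 104 in total. It does not bear on S2.2. The usable inputs are 160 infants accrued and losses of 15% and 7%, which add to 22%. That leaves 160 × 0.78 = 124.8 complete infants, against the 120 evaluable that the plan requires.

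**Assumed inputs.** The documents give no calprotectin SD, no week-3 to week-6 correlation, no expected effect and no timing of loss. I assume values standardised to SD 1, correlation ρ = 0.6, a true difference of 0.5 SD at both weeks, and 80 infants per arm.

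**Step 1: week-3 values discarded.** Late losses = 160 × total loss × share of the loss that falls after week 3. Week-3 values collected = complete infants + late losses.

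| Total loss | Share late | Week-3 values discarded | Week-3 values collected | Proportion |
|---|---|---|---|---|
| 22% | 25% | 8.8 | 133.6 | 6.6% |
| 22% | 50% | 17.6 | 142.4 | 12.4% |
| 22% | 75% | 26.4 | 151.2 | 17.5% |
| 7% (NEC only) | 25% | 2.8 | 151.6 | 1.8% |
| 7% (NEC only) | 75% | 8.4 | 157.2 | 5.3% |

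**Step 2: precision when loss is unrelated to calprotectin.** Let n be the infants per arm with a week-3 value and c those with both. For the group difference averaged over the two weeks:

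- complete pairs: variance = (1 + ρ)/c
- all data (maximum likelihood): variance = ½ × [(1 + ρ)²/n + (1 − ρ²)/c]

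In both cases c = 80 × 0.78 = 62.4, so the complete-pair variance is 1.6/62.4 = 0.02564 (SE 0.160).

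- All loss late, n = 80: ½ × (2.56/80 + 0.64/62.4) = 0.02113 (SE 0.145). Ratio 0.02564/0.02113 = 1.21.
- Half the loss late, n = 80 × 0.89 = 71.2: ½ × (2.56/71.2 + 0.64/62.4) = 0.02311 (SE 0.152). Ratio 0.02564/0.02311 = 1.11.

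**Step 3: bias when loss is related to calprotectin.** In simulated trials, the odds of gut-related loss after week 3 rise by a factor of 2.7 (assumed) per SD of the week-3 value. The true difference is 0.50 SD.

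| Scenario | Complete-pair estimate | Shortfall |
|---|---|---|
| Half the loss late; only the NEC share gut-related | 0.49 | 0.01/0.50 = 2% |
| All loss late; only the NEC share (7%) gut-related | 0.48 | 0.02/0.50 = 4% |
| All 22% late and calprotectin-related | 0.45 | 0.05/0.50 = 10% |

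The all-data likelihood estimate stays at 0.50 in these settings. That follows from the set-up, because loss was made to depend only on an observed value.

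**Step 4: when there is no bias, and when the direction changes.** A separate set of simulations used correlation 0.5 and log odds ratios of 1 and 2 per SD. With no true difference and the same loss mechanism in both arms, the complete-pair estimate was 0.00 and the rejection rate about 5%. With no true difference but twice the odds of loss in one arm, it moved away from zero, by 0.04 to 0.07 SD, and rejection was 6% to 8%.

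**Step 5: limits of the remedy.** If the 22% loss depends on the unobserved week-6 value instead, the all-data estimate is also biased: 0.48, against about 0.45 for complete pairs.

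**The case against.** A reader might infer that the plan restricts the analysis to infants with both samples. It does not say so. The restriction follows from the classical form of the named method; the same label is sometimes used for likelihood models that keep all available values, and the intent-to-treat statement points away from a deliberate completers analysis. What stands is that neither the model form nor the missing-sample rule is specified.

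A reader might also infer that the comparison is certainly biased, and toward no difference. Step 4 shows that both parts depend on conditions that the documents do not establish.

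Putting the whole 22% after week 3 and tying all of it to calprotectin is the extreme case. The plan's 22% covers the whole study, and an infant lost before week 3 has no value to waste. Only the 7% is attributed to NEC; the 15% has no stated link to gut inflammation. With half the loss late and only the NEC share gut-related, the shortfall is 0.01 SD against an SE of about 0.15.

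Nor does it follow that the named ANOVA cannot give week-specific results. A two-group, two-time analysis ordinarily includes group by time. The plan merely leaves open which contrast its promised estimate refers to.

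Finally, S2.2 is secondary, unpowered, and judged significant only descriptively. The logrank test would show a difference in withdrawal between arms, but it does not repair the calprotectin comparison.

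**Conclusion.** The point holds as a gap in specification with a cheap and better alternative. Read classically, S2.2 drops the week-3 value of every infant lost between weeks 3 and 6, roughly 9 to 26 values if 25% to 75% of a 22% loss is late. That inflates the variance of the averaged effect by about 11% (half the loss late) to 21% (all late).

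Bias is a risk and not a certainty. It needs loss related to calprotectin together with a true difference or unequal loss by arm. For a true 0.50 SD difference and an odds ratio of 2.7 per SD, the estimate ranges from 0.49 to 0.45, with the lower end reached only in the extreme case. All of these sizes rest on the assumed correlation, effect, loss mechanism and timing. The documents do not support a claim that the S2.2 result will be wrong, and the primary hypothesis is not affected.

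**What to change.** For S2.2, replace the ANOVA with a linear mixed model for repeated measures, fitted by REML with an unstructured covariance and terms for group, week and group by week. Include every randomized infant with at least one stool sample, and keep samples taken before a withdrawal. Analyse on the log scale if residuals are right-skewed. Report the group difference at week 3, at week 6 and averaged, each with a 95% confidence interval. Add a sensitivity analysis in which the missing week-6 values are allowed to differ from what the week-3 value predicts, over a stated range and separately by arm.

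The cost is a few sentences in the analysis plan and standard software, with no new data. The model assumes that week-6 values are missing at random given the week-3 value, which is weaker than what complete pairs require but may still fail; hence the sensitivity analysis. It does not recover infants lost before week 3, and it does not settle how deaths should be handled. The plan should state both limits.

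### P1.1 has an efficacy stop at 66 infants, but its P-value, 95% CI and 5% threshold ignore that look: about 6.2% type I error at the planned end instead of 5%

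*Combined protocol and SAP*

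**What the plan says.** The section on sample size and power plans one interim analysis of P1.1, "with first look after 66 evaluable subjects have been accrued". The rule is "If $|Z|>2.28$ we shall stop for significance". A value of |Z| below 1.12 triggers a review, but the text then excludes stopping for futility. If the trial does not stop, it goes on to 120 evaluable infants. No critical value for that final analysis is given.

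In the Statistical Analysis section, P1.1 is "compared between the two randomized treatment groups via a two-sided Welch-corrected T-test", and the interim analysis is referred back to the power section. The section promises actual P-values, and "each hypothesis will be accompanied by a point estimate and 95% confidence interval estimate for effect size". It labels P below 5% significant, for descriptive purposes. Nothing there separates P1.1, which is tested twice, from the secondary hypotheses. Nothing says how the Welch statistic becomes the Z of the stopping rule.

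**The concern.** A hypothesis that can be declared positive at either of two looks has two chances of a false positive. If 2.26% of the two-sided error is spent at the first look and the final test still uses 5%, the total exceeds 5%, and the ordinary 95% interval undercovers by the same amount under the null. A futility stop would have offset most of this, but the plan excludes one.

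The second issue is the size of the reported effect. A trial that stops early does so because its observed difference was large. The ordinary estimate is then too high on average, and the plan has no sentence telling the reader so. Aim 1 sets out to weigh risks against benefits, so the size of the intake gain matters as well as its significance.

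**Working it through.** **Inputs.** From the power section: control mean 72 mL/kg/d at 14 days, SD 65, target 108 (difference 36), two-sided 5%, 80% power, look at 66, cut-off 2.28, final size 120. Assumed: equal arms (33 then 60 per arm; the Randomization section aims for approximate balance), and a known SD of 65 for the normal calculations.

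**The plan's own figures.**
- Non-sequential size: 2 × (1.960 + 0.842)² × 65² / 36² = 51.2, so 52 per arm and 104 in total. This matches "To detect a 50% improvement to 108, we would require 104 evaluable subjects in a non-sequential design for Primary 1.1".
- Worst-case average size: 66 + 54 × max P(1.12 < |Z1| < 2.28) = 89.8, against the stated 89. This works only if the trial stops below 1.12. Without a futility stop the maximum is 66 + 54 × 0.977 = 118.8. The quoted 89 therefore belongs to a design with a futility stop, which the current text does not have.

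**Overall type I error.** The correlation of Z1 and Z2 is √(66/120) = 0.742.
- First look: P(|Z1| > 2.28) = 0.0226.
- Final look at nominal 5%: P(|Z1| ≤ 2.28 and |Z2| > 1.96) = 0.0390.
- Sum: 0.0616, about 6.2%. CI coverage under the null is 1 − 0.062 = 93.8%.
- With a binding stop below 1.12, the same 1.96 would give 5.2%. Most of the excess therefore comes from dropping the futility stop without resetting the final cut-off.
- The final cut-off that restores 5% with no futility stop is 2.088 (nominal P 0.0368).

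**Welch t in place of Z.** At 64 degrees of freedom P(|t| > 2.28) = 0.0259, against 0.0226 for the normal. In simulations with normal data, comparing the Welch t with 2.28 at the look gave 6.4% overall with a final Welch P < 0.05, and 6.6% with a final |t| > 1.96. With both looks on the Welch P-value scale (0.0226, then 0.0368), the simulated total was 5.0%.

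**Difference needed to stop early.** SE1 = 65 × √(2/33) = 16.00, and 2.28 × 16.00 = 36.5 mL/kg/d. At observed SDs of 45, 55 and 75 the figure is 25.3, 30.9 and 42.1.

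**Mean estimate after a favourable early stop.** δ + SE1 × φ(a)/(1 − Φ(a)), with a = 2.28 − δ/SE1.
- δ = 36: a = 0.030; 36 + 16.00 × 0.817 = 49.1. Chance of the stop 49%; coverage of the ordinary CI given the stop 95%.
- δ = 18: a = 1.155; 18 + 16.00 × 1.651 = 44.4. Chance 12%; coverage given the stop 80%.

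**Over all outcomes.** The bias of the ordinary estimate is 1.5 at δ = 18 and 2.9 at δ = 36, the largest among the true effects examined (0 to 45). Coverage runs from 93.8% to 95.1%.

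**What stage-wise ordering changes at 120.**
- Final Z = 1.96: ordinary 23.3 (0.0 to 46.5), P 0.050; adjusted 22.8 (−1.1 to 46.2), P 0.062.
- Final Z = 2.5: ordinary 29.7 (6.4 to 52.9); adjusted 28.1 (2.9 to 52.0).
- After a stop at the first look it changes nothing.

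**The case against.** Four points can be made for the plan.

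*The 5% rule is labelled descriptive, and the cited two-stage method may supply a final cut-off.* Both are possible. But the text gives no other criterion for P1.1 at 120, and the figure of 89 fits a design that stops below 1.12. A final cut-off built for that design would be about 1.987, which is too lenient once futility stopping is excluded.

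*The overall distortion is small.* This stands. Coverage stays within about 1.2 points of nominal, and the average bias is at most about 3 mL/kg/d. A reader might infer that the ordinary estimate is badly biased in general. It is not; the overestimation is concentrated in early stops.

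*The 36.5 threshold is not a floor.* A reader might infer that any early stop for benefit must report at least 36.5 whatever the truth. That holds only at an observed SD of 65, because Z uses the observed SD. About 26% of simulated early stops under the null showed a smaller difference. The figure is also on the 14-day mL/kg/d scale of the power section, whereas the analysis section names total weekly intake.

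*The mismatch between t and normal is minor and partly conjectural.* This also stands. Z is undefined, and converting the Welch P-value to Z is not excluded. Read literally, the mismatch adds about 0.3 points at the look. The documents do not support calling it a demonstrated error; they leave a gap that one sentence would close.

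Nor does a bias-adjusted estimate cure early-stop overestimation. The Whitehead adjustment lowers the conditional mean from 44.4 to 41.9 at a truth of 18 (2.5 of an excess of 26.4, about 10%) and from 49.1 to 46.9 at 36 (2.2 of 13.1, about 17%). It also lowers the already low average among trials that continue, from 29.1 to about 27.0 at a truth of 36. Making it the headline estimate is a preference, so it belongs beside the ordinary one.

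**Conclusion.** The concern holds in a limited form. As written, P1.1 has two chances of a positive result, and the reporting rules account for one. If P < 5% is applied at 120, overall type I error is about 6.2%, or 6.4% to 6.6% if the Welch t is set directly against 2.28 at the look. The ordinary CI covers about 93.8% under the null. After a favourable early stop the ordinary estimate is too large on average (about 49 for a true 36, about 44 for a true 18), and no caveat is planned.

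The error rates assume looks at 66 and 120 with equal arms, approximate normality of the test statistic, and no futility stopping in practice. They do not depend on the outcome scale. The mL/kg/d figures also depend on the planning SD of 65. The defect is modest in size, but it affects the primary hypothesis and can be fixed in the text alone.

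**What to change.** Add to the Statistical Analysis section, for P1.1 only:

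1. Significance, the P-value and the 95% CI come from a group-sequential method with stage-wise ordering that allows for the look at 66. With no futility stop, the equivalent final cut-off is about |Z| > 2.09 (nominal P about 0.037).
2. Both decisions are made on the Welch two-sided P-value: stop at the look if P < 0.0226, and apply the final cut-off on the same scale.
3. After an early stop, give the ordinary estimate with a statement that it is conditionally too large, and show a bias-adjusted estimate beside it as supportive. Note that stage-wise ordering leaves the first-look CI unchanged.

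The cost is a few sentences and standard group-sequential software; sample size and conduct do not change. The final threshold is slightly stricter: power at a difference of 36 falls from 86.5% (final 1.96) to 83.9% (final 2.088), still above the planned 80%. Stage-wise P-values at 120 also cannot fall below the 0.0226 spent at the look (a final Z of 3.0 gives 0.024), so the ordinary results are worth showing alongside.
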